HRPP	Human Research Protections Program
ICI	Immune Checkpoint Inhibitor
IDE	Investigational Device Exemption
IHC	Immunohistochemistry
IND	Investigational New Drug
IV (or iv)	Intravenously
MIBC	muscle invasive bladder cancer
MRI	Magnetic Resonance Imaging
MTD	Maximum Tolerated Dose
NACT	Neoadjuvant chemotherapy
NCI	National Cancer Institute
ORR	Overall Response Rate
OS	Overall Survival
PBMCs	Peripheral Blood Mononuclear Cells
pCR	Pathologic Complete Response
PD	Progressive Disease
PET	Positron Emission Tomography
PFS	Progression Free Survival
p.o.	per os/by mouth/orally
PR	Partial Response
PULSAR	Personalized ULtrafractionated Stereotactic Adaptive Radiotherapy

RCB	Residual Cancer Burden
RECIST	Response Evaluation Criteria in Solid Tumors
RFS	Recurrence Free Survival
SAbR	Stereotactic Ablative Radiotherapy
SAE	Serious Adverse Event
SCCC	Simmons Comprehensive Cancer Center
SD	Stable Disease
SGOT	Serum Glutamic Oxaloacetic Transaminase
SoC	Standard of Care
SPGT	Serum Glutamic Pyruvic Transaminase
WBC	White Blood Cells

STUDY SCHEMA

STUDY SUMMARY

Title	Checkpoint Inhibitor and Radiation Therapy in Bulky Node-Positive Bladder Cancer (CIRTiN-BC): A Phase II, Single-Arm Trial
Short Title	CIRTiN-BC
Protocol Number	STU-2021-0114
Phase	Phase I/II
Methodology	Single-arm safety/efficacy trial
Study Duration	36 months
Study Center(s)	Single center at UT Southwestern Medical Center, with potential expansion to Parkland Hospital and John Peter Smith Hospital
Objectives	To evaluate the safety and efficacy of PULSAR in patients with bulky node-positive bladder cancer on immune checkpoint inhibitor therapy due to ineligibility for or failure to respond to downstaging chemotherapy
Number of Subjects	27
Diagnosis and Main Inclusion Criteria	bladder cancer with bulky regional lymph node metastases, planning immune checkpoint inhibitor therapy due to ineligibility for downstaging chemotherapy or failure to respond to downstaging chemotherapy
Study Product(s), Dose, Route, Regimen	PULSAR (personalized ultrafractionated stereotactic ablative radiotherapy) 30 Gy in 3 fractions
Duration of administration	3 fractions at 12 - 16 day intervals
Reference therapy	standard of care with systemic therapy alone, followed by radical cystectomy if treatment response
Statistical Methodology	Proportion of patients completing the study will be calculated and the trial will be deemed successful if the number of patients completing the protocol exceeds the futility threshold of 60%. Progression-free survival, the secondary endpoint, will be estimated by the Kaplan-Meier method and compared with historic controls using the log-rank test.

1.0 BACKGROUND AND RATIONALE

1.1 Disease Background

Muscle invasive bladder cancer (MIBC) has high metastatic potential and warrants aggressive treatment. Standard-of-care treatment in MIBC involves platinum-based neoadjuvant chemotherapy (NACT) followed by radical cystectomy (RC) with pelvic lymph node dissection (PLND) and urinary diversion¹⁻³. Bladder-conserving chemoradiation therapy is an appropriate alternative in select patients, though it is used in only a minority of cases in the United States⁴. Bladder cancer carries significant morbidity and mortality and has been cited as the most expensive malignancy to manage, on a per-patient basis, in the United States^{5,6}.

Metastatic spread to regional lymph nodes is an adverse prognostic factor in bladder cancer. In several large case series reported without use of neoadjuvant chemotherapy, patients with pathologically positive lymph nodes (pN+) at radical cystectomy had 5-year overall or disease-specific survival rates of only 22-30%⁷⁻¹⁰. The addition of neoadjuvant chemotherapy (NACT) or downstaging chemotherapy (DCT) in patients with clinically positive lymph nodes (cN+) improves outcomes, particularly in those who achieve a pathologic complete response to DCT^{11,12}. However, patients who fail to respond to downstaging or neoadjuvant chemotherapy have an especially poor prognosis, with a 5-year overall survival rate of only 16% in one recent series¹³. It should also be noted that a significant proportion (up to 25-50%) of patients with bladder cancer are ineligible for chemotherapy due to medical comorbidities¹⁴.

We recently reviewed the outcomes of patients undergoing radical cystectomy at UT Southwestern with bulky cN+ bladder cancer¹⁵. Among the subset of patients who did not receive or failed to respond to DCT, the 2-year progression-free survival was only 30%, despite aggressive salvage treatment. Importantly, a majority of patients (84%) in the study received downstaging chemotherapy and all were medically eligible for chemotherapy. This suggests that chemo-ineligible patients presenting with cN+ disease were not offered curative treatment. Direct comparisons with historic literature are difficult, due to widely varying definitions of cN+ disease; however, the progression-free survival of our bulky cN+ cohort closely parallels that of the cN2-3 and cM1a cohorts within one large published series¹¹, confirming that our bulky cN+ cohort represents an especially high-risk population.

From the preceding data it is apparent that patients with cN+ bladder cancer who are ineligible for or who fail to respond to downstaging chemotherapy are an unfortunate group with particularly poor outcomes. One potential avenue for improvement is the combination of stereotactic ablative radiotherapy (SAbR) and immune checkpoint inhibitor (ICI) as downstaging therapy prior to radical cystectomy. We anticipate that patients will benefit from the demonstrated anti-tumor effects of both treatment modalities. Additionally, combining the immunomodulatory effects of SAbR with the stimulatory effects of ICI may result in a synergistic effect more beneficial than either modality alone.

1.2 Stereotactic Ablative Radiotherapy (SAbR) and Personalized Ultrafractionated Stereotactic Adaptive Radiotherapy (PULSAR)

Stereotactic Ablative Radiation (SAbR), also known as Stereotactic Body Radiation Therapy (SBRT), is defined by the American Society of Radiation Oncology as a precise and specialized form of cancer treatment “whereby high doses of radiation are delivered

in large fraction sizes over a short course of treatment, generally limited to 5 or fewer fractions.”¹⁶ Metastasis-directed therapy with SAbR has attracted interest in a variety of malignancies due to promising early clinical results and a favorable toxicity profile. In the Phase II SABR-COMET trial, patients with cancer (primarily breast, lung, colorectal, and prostate) and up to five sites of metastasis were randomized to receive metastasis-directed SAbR (8-30 Gy in 1-10 fractions) versus standard of care. The use of SAbR resulted in an improvement in 5-year overall survival from 18% to 42% ($p = 0.006$) and in 5-year progression-free survival from ~3% to 17% ($p = 0.001$)¹⁷. Grade ≥ 2 adverse events were noted in 29% of patients and treatment-related deaths in 4.5%¹⁸.

In the Phase II ORIOLE trial, men with prostate cancer and 1-3 sites of metastatic disease were randomized to receive metastasis-directed SAbR (20-48 Gy in 3-5 fractions) versus standard of care. SAbR resulted in improved progression-free survival (median not reached vs 5.8 months, $p = 0.002$) with no grade ≥ 3 toxic events¹⁹. These results of these trials support a significant recurrence-free and overall survival benefit for metastasis-directed SAbR in oligometastatic cancer.

There is limited data on the use of metastasis-directed treatment in urothelial carcinoma. In one report, 22 patients with oligometastatic urothelial carcinoma (64% with regional lymph node metastases) underwent conventional intensity-modulated radiation therapy (25-56 Gy) and achieved long-term (≥ 6 yrs) survival in 36%, with most representing patients with pelvic nodal disease²⁰. In another series, 19 patients with metastatic urothelial carcinoma received SAbR to a total of 25 different metastatic lesions and achieved a local control rate of 68%. No grade ≥ 3 toxic events were noted. More recently, in a small Phase I trial, patients with metastatic urothelial carcinoma received SAbR (24 Gy in 3 fractions) to a single metastatic lesion, either concurrently or sequentially with the immune checkpoint inhibitor pembrolizumab. One patient (6%) experienced a grade 3 adverse event. Four out of nine patients (44%) in the concurrent-treatment group had a clinical response in sites of disease other than the irradiated lesion²¹.

The use of SAbR in pelvic lymph nodes has been extensively described in the prostate cancer literature. Roughly 60% of the patients in the aforementioned ORIOLE trial had lymph node-only metastases and, as mentioned, none suffered major toxic events^{19,22}. The Phase II STOMP trial, in which 55% of patients had node-only metastases and 81% of patients in the intervention arm received SAbR, likewise reported no grade ≥ 2 adverse events²². Two additional retrospective case series recently described outcomes in patients undergoing SAbR for oligometastatic prostate cancer. In one series, 94 patients underwent SAbR (median 24 Gy in 3 fractions) to pelvic lymph nodes with a 14% rate of grade 1-2 toxicity and no grade ≥ 3 events²³. In a second series, 40 patients received SAbR (35-40 Gy in 5 fractions) to various sites of nodal metastasis (nearly all within the pelvis) with a single case of grade 2 and a single case of grade 3 toxicity²⁴. Based on these results, use of SAbR in pelvic lymph nodes appears to be safe and well tolerated, with only minimal toxicity.

A further refinement beyond conventional SAbR, developed at UT Southwestern, is personalized ultrafractionated stereotactic adaptive radiotherapy (PULSAR). PULSAR adapts to tumor shrinkage, minimizing radiation-associated side effects. The PULSAR dose schedule mimics the vaccine booster regimen by spacing out treatments, allowing for a full cycle of antigen presentation and immune response to occur before successive doses of radiation.

In this trial, we propose a shift in the paradigm in how radiotherapy is combined with immunotherapy. Current standards of delivering SAbR entail delivering 1 to 5 fractions, consecutively daily or every other day. We hypothesize that the delivery of radiotherapy can be optimized in patients receiving immunotherapy and propose a radiotherapy

paradigm, which we termed: Personalized Ultra-fractionated Stereotactic Adaptive Radiotherapy or PULSAR.

PULSAR sets its premise on delivering radiotherapy over intentionally longer, infrequent intervals between each radiation treatment, in contrast to historical schedules (i.e. daily fractions) in an effort to activate the immune system and avoid the potentially immunosuppressive effect from ablative radiotherapy. The interval between each fraction can be irregular, episodic, or triggered, depending on the response profile for each individual patient and can elicit additional tumor kill as well as an in situ vaccination booster, which, in combination with systemic immunotherapy, can synergize and improve disease control. Moreover, each radiotherapy fraction can be adapted in real time, depending on changes with the patient and disease status (e.g. anatomy, tumor microenvironment, systemic markers, patient status). This novel radiation treatment strategy has been supported by preclinical data in murine studies performed by our group (manuscript in preparation).

To our knowledge, the neoadjuvant use of SBRT with the new PULSAR regimen or without concomitant use of immune checkpoint inhibition for bladder cancer has not been studied previously. We will conduct our study of PULSAR in patients with locally advanced bladder cancer, as PULSAR is suited to target and kill primary and nodal sites, while providing an opportunity to prime the immune system with novel tumor-associated antigens and vaccinate the immune system in situ.

1.3 Immune Checkpoint Inhibitor Therapy

Immune checkpoint inhibitor (ICI) therapy has assumed increasing importance in the management of bladder cancer. ICI agents function to nonspecifically stimulate the patient's immune response and decrease tumor immune evasion by inhibiting negative regulators of the immune response. In bladder cancer, most interest has attached to monoclonal antibodies which block the immunosuppressive surface receptor PD-1 or its ligand PD-L1²⁵.

Three PD-1 or PD-L1 inhibitors (avelumab, nivolumab, and pembrolizumab) are FDA-approved for second-line use in platinum-refractory advanced bladder cancer, based on clinical trials which showed objective response rates of 15-20%²⁶⁻³⁰. Two agents (atezolizumab and pembrolizumab) are FDA-approved for first-line use in patients who are ineligible for platinum-based chemotherapy, based on clinical trials showing objective response rates of 25-30% in this setting^{31,32}. Finally, avelumab has recently gained FDA approval for use as maintenance therapy following initial response to chemotherapy in advanced/metastatic bladder cancer, with clinical trials demonstrating an improvement in median overall survival from 14 to 21 months³³.

More recent efforts have explored a role for ICI treatments in the neoadjuvant setting. Two clinical trials, ABACUS and PURE-01, explored the use of neoadjuvant atezolizumab and pembrolizumab respectively, and reported pathologic complete response (pCR, meaning ypT0 N0) rates of 31% and 37%, respectively^{34,35}. While several other ongoing trials exist in this space, only a single trial has enrolled significant numbers of patients with clinical node-positive disease. In this trial, NABUCCO, patients with cN+ disease represented 42% of total enrollment. Neoadjuvant treatment with dual ICI agents (the PD-1 inhibitor nivolumab and the CTLA-4 blocker ipilimumab) resulted in an overall pCR rate of 46%³⁶.

Given their widespread clinical use in bladder and other malignancies, the adverse effect profile of ICI agents is well characterized. In the second-line trials cited above, for example, grade ≥ 3 adverse events occurred in 5-18% of patients and most notably

included autoimmune reactions at various sites including pneumonitis, colitis, and hepatitis²⁶⁻³⁰.

In addition to the well described direct anti-tumor effects of SAbR and ICI treatment, mounting preclinical and clinical evidence also suggests a synergistic effect of the two modalities. SAbR has multiple immune-stimulating properties, including the induction of immunogenic tumor cell death and initiation of tumor antigen presentation³⁷⁻⁴⁰. Furthermore, SAbR causes local inflammation, which attracts dendritic cells to the tumor, thereby improving tumor neoantigen presentation^{41,42}. The promotion of immune anti-tumor activity by radiation has been linked to increased expression of tumor-infiltrating immune cells and MHC class I, dendritic cell activation and enhanced tumor antigen cross-presentation, T-cell receptor repertoire expansion, and increased PD-L1 expression. Therefore, therapy with SAbR, which increases PD-L1 expression by both the tumor and the immune cells, has the potential to induce responses in those patients that do not respond or progress after an initial response to an ICI. As discussed above, the PULSAR technique is designed to further improve the immunomodulatory properties of SAbR.

1.4 Study Rationale

The proposed study is a Phase I/II, single arm, single institution trial of PULSAR (next-generation SAbR) therapy prior to radical cystectomy in patients with bulky, clinically node positive bladder cancer who are planned to initiate ICI due to ineligibility for platinum-based chemotherapy or failure to achieve complete clinical response to platinum-based chemotherapy. Current NCCN guidelines recommend “downstaging systemic therapy” (i.e., downstaging chemotherapy and/or ICI) for such patients as standard of care, with consolidation radical cystectomy in patients who respond to treatment⁴³. However, our recent institutional experience demonstrates that even patients who do undergo radical cystectomy have poor outcomes, and patients who are medically ineligible for systemic chemotherapy are likely not being offered curative treatment at all¹⁵. Unfortunately, despite poor outcomes in cN+ patients, they are frequently excluded from clinical trials. For example, of the numerous trials involving the use of ICI agents in the neoadjuvant setting, only one (NABUCCO) enrolled significant numbers of cN+ patients and these still amounted to less than 50% of the total³⁶. There is therefore an urgent need for new clinical trials in this space.

Stereotactic ablative radiotherapy (SAbR) and immune checkpoint inhibitor (ICI) therapy both have demonstrated anti-tumor effects in the metastatic setting, as well as favorable and well characterized safety profiles. The rationale for adding PULSAR (next-generation SAbR) to ICI is that 1) the additive effect of both modalities is likely greater than either modality alone; 2) the morbidity and recovery period of radical cystectomy frequently preclude patients from receiving additional lines of treatment, and additional treatments are therefore likely best given prior to surgery; and 3) as detailed above, PULSAR may potentiate the effects of ICI by increasing tumor neoantigen exposure to immune surveillance and by increasing levels of PD-L1 expression within the tumor, thus enhancing response to ICI.

The rationale for proceeding with radical cystectomy after ICI + PULSAR treatment is that 1) radical cystectomy remains the standard of care in patients who respond to treatment and is felt to be the only potentially curative option in advanced disease; 2) cystectomy will debulk the primary tumor, thus reducing disease burden as well as the systemic effects of the immunosuppressive tumor microenvironment; and 3) other modalities including repeat transurethral resection and imaging are not sufficiently predictive of a complete response to treatment to justify omission of cystectomy⁴⁴.

Patients will be restaged prior to radical cystectomy and those with disease deemed unresectable (e.g., interval development of distant metastases or unacceptably high surgical risk) will be managed according to the standard of care for metastatic disease, i.e., without curative intent. It should be noted that patients on ICI frequently experience a “pseudoprogression” phenomenon in which tumor size transiently increases following treatment initiation due to tumor immune infiltration⁴⁵. Patients will therefore not be excluded from undergoing cystectomy solely on the basis of enlarging pelvic lymph nodes after ICI and RECIST criteria will not be applied in this setting.

In confining our analysis to patients with platinum-ineligible or platinum-refractory bulky cN+ disease, we wish to focus on a subset of patients with particularly poor outcomes and limited access to other modalities of treatment. Our hope is that combined-modality treatment with ICI + PULSAR + RC will increase the proportion of patients with bulky cN+ disease who undergo curative treatment, improve rates of pathologic complete response (pCR) prior to surgery, reduce rates of disease recurrence (which, in the context of bladder cancer, is an excellent proxy for cancer-specific survival), and ultimately improve patient quality of life without increasing short-term surgical complications.

1.5 Correlative Studies

No correlative studies are planned.

2.0 STUDY OBJECTIVES

2.1 Primary Objectives

2.1.1 To determine the feasibility of radical cystectomy after ICI + PULSAR in bulky cN+ bladder cancer patients who are ineligible for or fail treatment with platinum based chemotherapy.

2.2 Secondary Objectives

2.2.1 To determine the 2-year progression-free survival (PFS) in patients with cN+ bladder cancer in all enrolled patients, and in the subset of patients completing the full protocol of ICI + PULSAR + RC.

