2.3 Primary Endpoints

2.3.1 The primary endpoint of the study is feasibility of RC after ICI + PULSAR, defined as the proportion of enrolled patients who complete three courses of PULSAR followed by radical cystectomy while remaining on ICI therapy, within sixteen weeks of initiation of PULSAR. It is anticipated that reasons for protocol non-completion may include progression to nonresectable disease and patient intolerance of treatment.

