2.4 Secondary Endpoints

2.4.1 Progression free survival (PFS): Primary disease progression will be defined as any of the following. Progression-free survival will be measured from the date of the first PULSAR treatment.

1. Emergence of new sites of disease or locoregionally recurrent disease as defined by RECIST 1.1 criteria.

2. Pathologic demonstration of recurrent or metastatic disease (e.g. core needle biopsy, fine needle aspirate, diagnostic peritoneal biopsy).
3. Initiation of a patient on palliative or salvage treatment due to clinical concern for disease progression.
4. For patients with intraoperative concern for grossly incomplete disease resection (R2), the date of the first postoperative imaging study showing disease progression by RECIST 1.1 criteria (i.e., 20% increase in the sum of the diameters of all lesions, with an absolute increase of at least 5 mm; or the appearance of any new lesion).

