4.0 TREATMENT PLAN

4.1 PULSAR: Dose and Techniques

Patients are eligible for the trial if they have bulky, clinically node-positive (cN+) bladder cancer and have either recently initiated (within \leq 1 week) or are planned to initiate immune checkpoint inhibitor (ICI) therapy due to either 1) ineligibility for/refusal of platinum-based downstaging chemotherapy; or 2) failure to achieve a complete clinical response to platinum-based downstaging chemotherapy. Patients will initiate PULSAR treatment 1-2 weeks after initiating ICI. PULSAR will be administered in 3 fractions of 12 Gy each (36 Gy total) at 12-16 day intervals and patients will undergo radical cystectomy with bilateral extended pelvic lymph node dissection within 4-8 weeks after completion of PULSAR. ICI therapy will be administered according to the FDA-approved dosing route and schedule and will be continued during PULSAR treatments.

PULSAR treatment will be initiated 1-2 weeks after the patient is initiated on an FDA-approved ICI agent. PULSAR will be administered in 3 fractions of 12 Gy each at 12-16 day intervals. Target areas will include the region of the bladder containing the primary tumor (confirmed, if necessary, on office flexible cystoscopy at UTSW) and to up to five targetable, pathologically enlarged bulky lymph nodes (as deemed feasible by the treating radiation oncologist). Non-enlarged pelvic lymph nodes will be spared to minimize adverse effects on the tumor immune response.

4.1.1 PULSAR will be delivered with the targeting, planning, and directing of treatment fields guided to a target based on known 3D coordinates related to reliable fiducial markers. This differs from conventional radiation therapy in which treatment is guided by skin or bony landmarks assumed to correlate to the target volume based on the initial simulation. Treatment will account for inter/intra-fractional errors with careful dosimetry that delivers an ablative dose to the involved lesions while respecting normal tissue constraints. In the event that fiducial placement is deemed unfeasible or unsafe, or would result in an unacceptable delay in treatment, fiducial placement may be omitted and targeting based on a combination of pre-treatment imaging and findings on flexible cystoscopy.

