5.4 Time and Events Table

	Screening	PULSAR Q12-16d x 3 fractions	Post PULSAR, pre RC	Post RC (30 days)	Post RC (90 days)	Follow up q6mo x 2 yrs
Procedures						
Informed Consent	X					
Eligibility verification	X					
History and Physical Exam	X	X	X	X	X	
Performance Status	X	X	X	X	X	
(Re)staging Imaging ¹	X		X		X	
Toxicity Evaluation		X	X	X	X	
Blood Draw ²	X	X	X	X	X	

Pregnancy Test (if applicable) ³	X					
PULSAR treatment ⁴		X				
Chart review / recurrence status						X

¹ CT or MRI with IV contrast, if possible. Imaging to determine eligibility must have been performed within **60 days of enrollment**. All imaging used within the study represents standard of care. Additional imaging may be obtained at the treating clinician's discretion.

² Blood draws after surgery represent standard of care

³ Only in females of child-bearing potential, as defined in section 3.1.

⁴ SAbR treatments to be administered in three fractions at 12-16 day intervals.

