6.1.6 Progression-Free Survival

Progression-free survival (PFS) is defined as the duration of time from start of PULSAR treatment to time of progression. Progression is defined as any of:

1. Radiologic disease progression, as defined by RECIST 1.1 criteria above.
2. Pathologic demonstration of recurrent or metastatic disease (e.g. core needle biopsy, fine needle aspirate, diagnostic peritoneal lavage).
3. Initiation of a patient on salvage or palliative treatment due to clinical concern for disease progression.
4. For patients with documented concern (by the operating surgeon) for grossly incomplete disease resection (R2) including bulky unresectable lymph nodes, the date of the first postoperative imaging study showing disease progression by RECIST 1.1 criteria.

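### PFS in the completer subset is timed from first PULSAR, before completion can be known, so its 2-year figure is biased upward in expectation

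*Combined protocol and SAP*

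**What the plan says.** Section 2.2.1 sets the secondary objective as 2-year PFS in everyone enrolled "and in the subset of patients completing the full protocol of ICI + PULSAR + RC".

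The time origin appears twice. Section 2.4.1: "Progression-free survival will be measured from the date of the first PULSAR treatment". Section 6.1.6: "Progression-free survival (PFS) is defined as the duration of time from start of PULSAR treatment to time of progression". Neither gives the completer subset a different origin.

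Completion is a later event. Three fractions are given 12 to 16 days apart (section 5.4), and cystectomy follows "within 4-8 weeks after completion of PULSAR" (section 4.1). The primary endpoint in section 2.3.1 requires all of this "within sixteen weeks of initiation of PULSAR". Section 2.2.1 does not restate that limit, so I take completion as 2.3.1 defines it.

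Progression can prevent completion. Section 2.3.1: "It is anticipated that reasons for protocol non-completion may include progression to nonresectable disease and patient intolerance of treatment". Section 1.4 says that patients found unresectable at restaging, for example with new distant metastases, are managed without curative intent.

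Sections 9.2 and 9.3 contain no landmark, no cystectomy origin, no time-dependent handling and no descriptive label for the subset.

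**The concern.** Membership of the subset is decided at cystectomy, but follow-up is counted from first PULSAR. During the weeks between, a future completer cannot have had progression that rules out surgery. Anyone who does have it leaves the subset and takes the event along. The same occurrence can be both a PFS event and the reason for exclusion: palliative treatment started because progression is suspected is an event under 2.4.1, and it is also the route that section 1.4 describes for unresectable disease.

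The completer figure is thus expected to exceed the all-enrolled figure even if neither PULSAR nor surgery changes the course of disease. Because this is a named secondary objective, the gap between the two figures could be read as a benefit of finishing the regimen.

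**Working it through.** **The plan's own figures.** The documents give no expected PFS for completers, so there is no subset figure to reproduce. The 90% power in section 9.2 for the PFS endpoint (30% against 57%, 24 patients, one-sided alpha 0.10) does reproduce: an exact binomial rule of at least 11 of 24 has alpha 0.074 and power 0.904. That says nothing about the size of this bias.

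**Time from first PULSAR to cystectomy**
- First to third fraction: 2 × 12 = 24 to 2 × 16 = 32 days.
- Third fraction to surgery: 28 to 56 days.
- Total by schedule: 24 + 28 = 52 to 32 + 56 = 88 days (7.4 to 12.6 weeks).
- Upper limit in 2.3.1: 16 × 7 = 112 days.

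**Guaranteed time alone.** Assumptions: 2-year PFS from first PULSAR is 30% (the historic figure in 9.3), the hazard is constant, every event before surgery disqualifies, and all completers have surgery on day t.

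h = −ln(0.30)/730.5 per day; S(t) = exp(−h·t); completer 2-year PFS = 0.30/S(t).

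| Surgery on day | S(t) | Completer 2-year PFS | Shift |
|---|---|---|---|
| 52 | 0.918 | 32.7% | 2.7 points |
| 88 | 0.865 | 34.7% | 4.7 points |
| 112 | 0.831 | 36.1% | 6.1 points |

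From a true 57% the same formula gives 59.3%, 61.0% and 62.1%.

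**Hazard shape.** The documents do not give it. For a Weibull curve with assumed shape k, completer PFS = 0.30/exp{ln(0.30)·(m/24)^k}, with m the months to surgery. Over the same three days, k = 0.7 (early events) gives 36.3% to 41.5% and k = 1.5 (late events) gives 30.7% to 32.2%. The range is about 1 to 12 points.

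**Guaranteed time and selection together.** If every non-completer progresses by 2 years, all patients who are progression-free at 2 years are completers. The completer figure is then 0.30/c at completion rate c:
- c = 0.90 (target): 0.30/0.90 = 33.3%
- c = 0.80: 0.30/0.80 = 37.5%
- c = 0.60 (futility bound): 0.30/0.60 = 50%

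If only half of non-completion is progression, and the other non-completers fare as completers do, the figure is 0.30/{1 − 0.5(1 − c)}: 31.6% at c = 0.90 and 37.5% at c = 0.60.

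The two sets of figures must not be added. Under the first set of assumptions S(t) is also the highest possible completion rate, so 34.7% and 36.1% imply completion of at most 86.5% and 83.1%. At 90% completion the ceiling is 33.3%.

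**Follow-up available for a new origin.** Section 4.11 follows PFS for two years from first PULSAR. From cystectomy that leaves 730 − 112 = 618 to 730 − 52 = 678 days, about 20 to 22 months.

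**The case against.** The strongest case on the other side has four parts.

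- **The subset is secondary to a sound figure.** Section 2.2.1 names all enrolled patients first, so readers see the unconditioned estimate alongside. Sections 9.2 and 9.3 attach no hypothesis or power to the subset. This stands and limits the consequence, but the subset figure remains a stated objective with no label or correction.
- **The bias is small beside the noise.** With about 22 completers (0.9 × 24 = 21.6), the standard error at 30% is √(0.30 × 0.70/22) = 0.098, a 95% half-width of about 19 points. This stands: the completer figure need not exceed the all-enrolled figure in the realised data. The bias is still of known direction, and more patients would not reduce it.
- **Not all worsening disqualifies.** Nodal enlargement alone does not bar cystectomy (section 1.4), pelvic nodes are not evaluable at the pre-surgery scan (6.1.2), and 5.5.4 lets the investigator continue treatment after progression. This stands, so the guaranteed-time figures, which let every early event disqualify, lean high. Distant or unresectable progression still excludes.
- **The historic series is also conditioned on surgery.** Section 1.1 describes patients who underwent cystectomy, so completers might look like the natural match. But the documents do not state that series' time origin. If it is cystectomy, completers timed from first PULSAR carry extra event-free weeks on the trial side only. The documents cannot settle which comparison is fairer.

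**Conclusion.** The point holds. As written, the plan yields a completer 2-year PFS that is biased upward in expectation, because membership requires about 7 to 13 weeks by schedule, and 16 at most, without disqualifying progression. Guaranteed time alone is worth about 3 to 6 points on a 30% base under a constant hazard with every pre-surgery event disqualifying. The true base rate, the hazard shape and the share of non-completion due to progression are assumptions.

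Three stronger readings are not supported:

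- A reader might infer a 20-point immortal-time gain. The 50% figure is an upper bound on guaranteed time and selection combined. It needs completion at the futility bound and progression in every non-completer, whereas 2.3.1 also names intolerance and 1.4 names surgical risk. Moving the clock does not remove the selection part.
- A reader might infer that the trial's PFS result as a whole is compromised. The all-enrolled PFS is not conditioned on surgery, and the primary endpoint is a completion proportion; neither has this bias.
- A reader might infer that the formal log-rank test is biased. Section 9.3 does not say which trial population enters it, so that is possible but not established.

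**What to change.** Amend 2.2.1, 2.4.1, 6.1.6 and 9.3 together. Leaving 6.1.6 unchanged would create a contradiction.

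- Keep first-PULSAR timing for the all-enrolled analysis.
- For completers, choose one of two forms. (a) Time PFS from cystectomy and report it at the horizon that 4.11 supports, about 20 months; a 2-year post-cystectomy figure is not observable without longer follow-up. (b) Use a landmark at 16 weeks, when completion status is known for everyone: take completers who are progression-free then and follow them to 24 months from first PULSAR.
- Label the result descriptive and conditional on reaching surgery. State that its difference from the all-enrolled curve is not evidence of benefit from completing the regimen.
- State in 9.3 that a completer curve timed from first PULSAR will not be tested against the historic 30%, because that series' time origin is not given.

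The cost is mainly wording, and either form fits the planned follow-up. The price is that the subset and overall estimates sit on different clocks, and that the subset has a shorter horizon under (a) or loses completers who progress before week 16 under (b). Neither form removes the selection of better-prognosis patients, which is why the label matters.
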